5.7. Schedule of Activities

This project is expected to be implemented for 6-15 months for individual sites depending on the allocated subject size.

CLINICAL STUDY PROTOCOL

Title: Multi-national, multi-center randomized controlled trial to evaluate the clinical utility of non-invasive endometrial receptivity test (ora™) in patients with implantation failure

Doc. No.	ORA-PTL-2024-01
Version	1.0
Date	2024/01/10

6. Risk and benefit analysis

The execution process of this study follows the standard procedures of in vitro fertilization (IVF), except for the blood specimen collection for endometrial receptivity testing. Rigorous standard operating procedures have been established for the specimen collection process, specimen storage, and specimen transportation. Only relatively sensitive subjects may experience discomfort during blood specimen collection, but noticeable improvement is observed after a period of rest.

7. Statistical considerations

7.1. Sample size calculation

The sample size calculation for the two-armed endpoint suggests that obtaining data from 650 participants (325 subjects for each group). This sample size is adequate to detect a 10% difference in clinical pregnancy outcomes between groups given an alpha level of $p < 0.05$ and a power of 0.8 and using 50% anticipated LB in the control arm (based on current success rates among euploid embryo transfers conducted with standard timing protocol). Accounting for 10-20% dropout rate, the goal is to enroll 800 subjects in total.

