3.3. Study Endpoints

(a) Primary Endpoint

Clinical pregnancy, defined as presence of one or more intrauterine gestational sacs after 6 weeks estimated gestational age.

(b) Secondary Endpoint

- 1) Ongoing pregnancy, defined as presence of fetal heartbeat after 12 weeks of gestation.
- 2) Live birth, defined as baby survival after 20 weeks of gestation.
- 3) Abortion and miscarriage rates.
- 4) Frequency and intensity of adverse events (AEs).

CLINICAL STUDY PROTOCOL

Title: Multi-national, multi-center randomized controlled trial to evaluate the clinical utility of non-invasive endometrial receptivity test (ora™) in patients with implantation failure

Doc. No.	ORA-PTL-2024-01
Version	1.0
Date	2024/01/10

4. Study Population

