7.2. Data Evaluation and Statistical Considerations

- (a) The outcome of clinical pregnancy and live birth rate, etc. per transfer will be compared between the study and control groups by chi-square analysis.
- (b) The quantitative outcomes such as gestational age and BMI, etc. will be compared between treatment groups by the Mann-Whitney U test.

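### Section 7.1 claims 80% power for 325 per arm, but the planned chi-square test has about 73%, and the control rate is labelled for another endpoint

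*Protocol*

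**What the plan says.** Protocol section 7.1 sets the evaluable sample at "obtaining data from 650 participants (325 subjects for each group" and states: "This sample size is adequate to detect a 10% difference in clinical pregnancy outcomes between groups". The error rates are "given an alpha level of $p < 0.05" "and a power of 0.8". The control assumption is introduced as "using 50% anticipated LB in the control arm (based on current success rates among euploid embryo transfers conducted with standard timing protocol". Enrolment follows from "Accounting for 10-20% dropout rate, the goal is to enroll 800 subjects in total".

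Section 7.2 gives the analysis: outcomes "per transfer will be compared between the study and control groups by chi-square analysis". Neither section mentions a one-sided test.

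Section 3.3 defines the primary endpoint: "Clinical pregnancy, defined as presence of one or more intrauterine gestational sacs after 6 weeks estimated gestational age". Live birth is listed there separately, as a secondary endpoint.

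**The concern.** Section 7.1 gives every input needed to recompute the sample size, and the result does not agree with the planned test. A chi-square test on a two-by-two table rejects for a difference in either direction, so at 0.05 it is equivalent to a two-sided z test. On that footing 325 per arm is too few for 80% power.

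The control rate raises a second problem. The calculation is for clinical pregnancy, yet the 50% is labelled LB. Its stated basis is euploid transfers with standard timing, with no restriction to women who have already had a failed euploid or low-level mosaic transfer, which section 4.2 requires. The protocol therefore gives no control rate for its own primary endpoint in its own population.

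At stake is the power claim for the primary comparison. Ethics committees and sites are told that the trial has a 20% chance of missing a 10-point benefit when the chance is nearer 27%, and a non-significant result would carry less weight against the test than readers would suppose.

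**Working it through.** **Inputs.** From section 7.1: control rate p1 = 0.50; difference 10 points, so p2 = 0.60 (0.40 gives the same n); alpha 0.05; power 0.80; 325 per arm; 800 enrolled; dropout 10–20%. From section 5.6: 1:1 allocation. From section 7.2: chi-square test.

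**Reproducing 325.** The usual formula per arm, with pooled rate p = 0.55, is

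n = [z_α·√(2p(1−p)) + z_β·√(p1(1−p1) + p2(1−p2))]² / (p2−p1)²

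with √(2·0.55·0.45) = √0.495, √(0.25+0.24) = √0.49 and z_β = 0.8416. The continuity-corrected size is n_cc = (n/4)·[1 + √(1 + 4/(n·|p2−p1|))]².

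| Calculation | n per arm | with continuity correction |
|---|---|---|
| Two-sided 0.05 (z = 1.960) | (1.3790 + 0.5891)²/0.01 = 387.3 → 388 | 407.1 → 408 |
| One-sided 0.05 (z = 1.645) | (1.1573 + 0.5891)²/0.01 = 305.0 → 305 | 324.7 → 325 |

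Unpooled variance gives 385 (two-sided) or 303 (one-sided); the arcsine method gives 388 or 305. Of the variants tried, only the one-sided calculation with continuity correction returns 325.

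**Power of the planned test at 325 per arm, 50% versus 60%, two-sided.**

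- Normal approximation: Φ[(0.10 − 1.960·√(0.495/325)) / √(0.49/325)] = Φ(0.0235/0.0388) = Φ(0.605) = 0.728.
- Exact binomial enumeration of the Pearson chi-square: 0.737.
- Exact enumeration with Yates correction: 0.711.

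Solving the approximate power equation for the difference detectable with 80% power from a 50% control rate gives 10.9 points.

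**Enrolment of 800.**

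- 10% dropout: 800 × 0.90 = 720, or 360 per arm; power 0.771 by approximation.
- 20% dropout: 800 × 0.80 = 640, or 320 per arm; power 0.721 (exact 0.726).
- Dropout at which 650 remain: 1 − 650/800 = 18.75%. At 20% dropout, 650 evaluable requires 650/0.80 = 812.5, or 813 enrolled.
- The 776 evaluable needed for 80% power would allow a loss of only 1 − 776/800 = 3%.

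**Sensitivity to the control rate.** Exact two-sided power for a 10-point gain at 325 per arm:

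| Control rate | 40% | 45% | 50% | 55% | 60% | 65% | 70% |
|---|---|---|---|---|---|---|---|
| Power | 0.737 | 0.736 | 0.737 | 0.741 | 0.766 | 0.797 | 0.840 |

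The protocol gives no clinical pregnancy rate, so these control rates are assumptions. Power reaches 80% only from about 65–66%.

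**The case against.** The best defence is that 325 is not a slip: it is exactly the one-sided, continuity-corrected figure, and a one-sided 0.05 test at 325 per arm does have the claimed power (0.822 by approximation, 0.800 with correction). The protocol leaves sidedness unstated, so reading alpha as two-sided is an inference. This probably explains where the number came from, but it does not make the text consistent. No section states a one-sided test, and the named test has no direction. If one-sided was intended, both sections need amending.

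A second defence concerns the control rate. In the same women, clinical pregnancy cannot sensibly be rarer than live birth, so correcting the endpoint alone would move the rate up from 50% and narrow the shortfall. That is fair, and the gap closes near 65%. The protocol offers no support for a rate that high, however, and a prior failed transfer may pull the rate the other way. A rate of 40% leaves the power for a 10-point gain unchanged.

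Two further objections stand in part. The source of the 50% is not described closely enough to know that it excludes women with a prior failure; the protocol simply does not show that it applies to them. And the dropout shortfall is small: 10 subjects, at the upper end of the range only, costing about one point of power.

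**Conclusion.** The concern holds. With the chi-square test of section 7.2 read as two-sided at 0.05, 325 per arm gives about 73% power for 50% versus 60% (0.728 approximate, 0.737 exact, 0.711 with Yates), not 80%. The stated 80% applies to a difference of about 10.9 points. Across the protocol's own dropout range, enrolling 800 gives 72% to 77%. The power conclusion assumes two-sided testing and a control rate below about 65%; it would fall away if a one-sided 0.05 test were stated and justified. The endpoint mismatch does not depend on sidedness: a rate labelled live birth is used to power clinical pregnancy. The dropout figure is a minor correction.

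**What to change.** Keep the enrolment target and rewrite section 7.1 so that it:

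- states two-sided alpha 0.05, 325 evaluable per arm, and about 73% power for 50% versus 60%, or equivalently 80% power for about 10.9 points;
- replaces the LB rate with the expected control clinical pregnancy rate in women with a prior failed transfer, gives its basis, and shows power over a range such as 40–60%, extended upwards if a higher rate is plausible;
- says that 800 covers dropout up to 18.75%, not 20%.

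This costs some rewording and a less favourable power figure, with no extra patients and no change to procedures.

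If a one-sided 0.05 test was intended, sections 7.1 and 7.2 must both say so, justify it and name a directional test. If the sponsor prefers to keep 80% power for 10 points with a two-sided test, the price is 776 evaluable subjects: 776/0.90 → 863 enrolled at 10% dropout, or 776/0.80 = 970 at 20%.

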7.2. Data Evaluation and Statistical Considerations

- (a) The outcome of clinical pregnancy and live birth rate, etc. per transfer will be compared between the study and control groups by chi-square analysis.
- (b) The quantitative outcomes such as gestational age and BMI, etc. will be compared between treatment groups by the Mann-Whitney U test.

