Inclusion/Exclusion Criteria :

Inclusion Criteria:

1. Patients who have at least one implantation failure with a euploid or low-level mosaic (< 30%) embryo transfer in the past two years.
2. Females within 28-45 years old.
3. Those who agree to undergo one mock cycle for ora™ test and execute single frozen embryo transfer in the later cycle.
4. Those who has at least one remaining euploid or low-level mosaic (< 30%) embryo.

Exclusion Criteria:

1. Known uterine factor (such as endometriosis, uterine fibroids) impacting the endometrium.
2. Presence of any clinically relevant systemic disease (such as immune disease) that contraindicates assisted reproductive technology.
3. Body mass index (BMI) exceeds than 30 kg/m².

Statistical Methodology:

1. The outcome of clinical pregnancy, ongoing pregnancy and live birth rate per transfer will be compared between the study and control groups by chi-square analysis.
2. The quantitative outcomes such as gestational age and BMI, etc. will be compared between treatment groups by the Mann-Whitney U test.

CLINICAL STUDY PROTOCOL

Title: Multi-national, multi-center randomized controlled trial to evaluate the clinical utility of non-invasive endometrial receptivity test (ora™) in patients with implantation failure

Doc. No.	ORA-PTL-2024-01
Version	1.0
Date	2024/01/10

2. Introduction

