4.4. Withdrawal criteria

- (a) During the research process of this research project, all subjects can unconditionally choose to withdraw.

	CLINICAL STUDY PROTOCOL	Doc. No.	ORA-PTL-2024-01
	Title: Multi-national, multi-center randomized controlled trial to evaluate the clinical utility of non-invasive endometrial receptivity test (ora™) in patients with implantation failure	Version	1.0
		Date	2024/01/10

5. Study Procedures

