5.1. Overall Design

This study aims to enroll up to 800 subjects who have experienced at least one implantation failure with a euploid or low-level mosaic (< 30%) embryo transfer in the past two years. Subjects should have at least one euploid or low-level mosaic (< 30%) embryo for the study. Subjects will be randomly assigned to either the control or study group. In the control group, subjects will simultaneously provide blood samples for the ora™ test and undergo Hormone Replacement Therapy (HRT) frozen embryo transfer during the standard implantation window (day 5 of progesterone supplementation: P+5/120 hours). In the study group, subjects will provide blood samples for the ora™ test during a mock HRT cycle; in the subsequent cycle, the subject will undergo HRT frozen embryo transfer during the period which the implantation window is confirmed as “Receptive” by ora™’s analysis. The study aims to compare pregnancy outcomes to evaluate whether ora™ timing offers clinical advantages to the patients.

Control Group: Euploid embryo transfer at standard implantation window (day 5 of progesterone supplementation: P+5/120 hours)

Study Group: Mock cycle followed by euploid embryo transfer at implantation window confirmed as “Receptive: by ora™’s analysis.

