5.6. Research Process

(a) Randomization:

After signing the ICF, the investigator will assign a **subject code** to each enrolled subject. This subject code will consist of two parts: the center identification number and the subject identification number. For instance, TW01-001.

- 1) The center identification number is structured using the first two letters of the country name followed by a two-digit site number. Examples include TW01, TW02, SG01, JP01, etc.
- 2) Within each age category at each center, subjects will receive a subject identification number assigned based on their order of inclusion in the study. The first subject enrolled will be labeled as 001, followed by 002, and so forth, maintaining chronological order.

Once the subject receives the unique subject code, the subject will be randomized to one of the two study groups through a simple 1: 1 randomization program stratified by center (to avoid bias). The randomization number will be assigned to each subject included in the study, as well as their corresponding group. The randomization program will be set up by the Inti Inc., Taiwan.

For example, the randomization process for a subject attending the initial clinical site in Taiwan:

Subject code	Randomization number	Group
TW01-001	1	Control
TW01-002	2	Study
TW01-003	3	Study
TW01-004	4	Control
TW01-005	5	Control
TW01-006	6	Study

CLINICAL STUDY PROTOCOL

Title: Multi-national, multi-center randomized controlled trial to evaluate the clinical utility of non-invasive endometrial receptivity test (ora™) in patients with implantation failure

Doc. No.	ORA-PTL-2024-01
Version	1.0
Date	2024/01/10

- (b) Subjects will undergo the hormone replacement therapy (HRT) in a frozen embryo transfer (FET) cycle. The HRT treatment cycle will be performed following medical criteria and in accordance with the usual practice of the clinic and the doctors. Ideally, the subjects in the control and study groups should follow identical drug prescription program.
- (c) Endometrial receptivity test by ora™:
- 1) Study group subjects will undergo blood sampling for the ora™ test on the fifth day of progesterone administration in a **mock cycle** (120 ± 3 hours after the first progesterone injection); the control group subjects will undergo blood sampling for the ora™ test and frozen embryo transfer at the standard time (120 ± 3 hours after the first progesterone injection) for data collection.

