 - 2) The collected blood samples will be processed into plasma by the researchers, and these samples will then be sent to the Inti Service Laboratory in Taiwan for an endometrial receptivity test. The results, indicating the receptivity timing as determined by ora™, will be provided 10 days later. The results include:
 - a. Receptive Phase: At the time of blood draw, it is the optimal Window of Implantation (WOI) for embryo implantation. It is recommended to perform embryo implantation at the sampling time point.
 - b. Pre-Receptive: At the time of blood draw, it is before the optimal Window of Implantation (WOI). The endometrium is not yet ready for embryo implantation. It is suggested to delay the embryo implantation window by 24 hours.
 - c. Post-Receptive: At the time of blood draw, the endometrium has passed the optimal time for embryo implantation. It is recommended to advance the embryo transfer time by 24 hours.
 - 3) Any subject whose blood sample does not provide adequate information to recommend timing for FET will be withdrawn from the study.

CLINICAL STUDY PROTOCOL

Title: Multi-national, multi-center randomized controlled trial to evaluate the clinical utility of non-invasive endometrial receptivity test (ora™) in patients with implantation failure

Doc. No.	ORA-PTL-2024-01
Version	1.0
Date	2024/01/10

(d) Frozen embryo transfer

On the day of embryo transfer, one of the subject's vitrified, euploid blastocysts will be thawed, and the subject will undergo single embryo transfer. **The frozen embryo transfer in the study group should follow the exact same drug prescriptions and dosage without deviation from the mock cycle.**

- 1) If the subject is assigned to the control group, a single embryo transfer will be performed on the subsequent cycle after randomization. The transfer timing follows the standard HRT protocol at 120 ±3 hours post initiation of progesterone.
- 2) If the subject is assigned to the study group, a single embryo transfer will be performed on the HRT cycle after the mock cycle. The transfer timing is based on the implantation window indicated by ora™ test results.

(e) Results confirmation

- 1) Approximately 10 days following implantation, a serum hCG concentration will be detected.
- 2) Around 6 weeks after estimated gestational age, an ultrasound will be performed to assess the presence of a gestational sac, providing an estimate of clinical pregnancy.

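### Clinical pregnancy is compared per transfer, a denominator set after randomisation by a route that differs by arm, so randomisation no longer guarantees comparable groups; any bias may have either sign or be zero

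*Protocol*

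**What the plan says.** Section 3.3 makes clinical pregnancy the primary endpoint. Section 7.2(a) fixes its denominator and test: "The outcome of clinical pregnancy and live birth rate, etc. per transfer will be compared between the study and control groups by chi-square analysis". The synopsis, under Statistical Methodology, gives the same rule: "The outcome of clinical pregnancy, ongoing pregnancy and live birth rate per transfer will be compared between the study and control groups". The protocol names no comparison of all randomised women and gives no rule for a randomised woman who has no transfer.

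Randomisation comes early. Section 5.6(a), after consent and coding: "Once the subject receives the unique subject code, the subject will be randomized to one of the two study groups".

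The routes from there to transfer differ:

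- **Control arm.** Transfer takes place in the next cycle (5.6(d)), and sampling coincides with it. Section 5.1: "subjects will simultaneously provide blood samples for the ora™ test and undergo Hormone Replacement Therapy (HRT) frozen embryo transfer".
- **Study arm.** Section 5.1: "subjects will provide blood samples for the ora™ test during a mock HRT cycle; in the subsequent cycle" they have their transfer. Between the two lies the laboratory result (5.6(c)): "The results, indicating the receptivity timing as determined by ora™, will be provided 10 days later".

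Two rules let women leave. Section 4.4: "all subjects can unconditionally choose to withdraw". Section 5.6(c)3): "Any subject whose blood sample does not provide adequate information to recommend timing for FET will be withdrawn from the study".

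**The concern.** Randomisation makes the two sets of randomised women comparable. It does not do so for the subsets who reach transfer, because reaching transfer is an event after allocation. Here the study arm has an additional cycle, an additional procedure and a wait in which a woman can leave before she is counted. The inadequate-sample rule also acts before transfer in that arm, whereas in the control arm it can act only once the transfer has been done.

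Bias arises in either of two ways. The arms may lose different numbers of women before transfer, and those women differ in prognosis from the rest. Or the arms may lose women of different prognosis, even in equal numbers. Part of an observed difference would then reflect who reached transfer and not the timing of transfer.

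A per-transfer rate also cannot show whether the test strategy leads fewer women to a transfer, which bears on the stated objective of clinical utility.

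**Working it through.** **The plan's own figure.** Section 7.1 gives 325 per group for 50% and a 10-point difference, alpha 0.05, power 0.8. The usual formula is n = [z_a·√(2·p̄·(1−p̄)) + z_b·√(p1(1−p1)+p2(1−p2))]² / d², with p̄ = 0.55 and d = 0.10.

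- One-sided: (1.645 × 0.7036 + 0.842 × 0.7)² / 0.01 = 305; with continuity correction, 325.
- Two-sided: 388; with continuity correction, 408.

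So 325 is reproduced only as a one-sided test with continuity correction. Section 7.1 does not state the sidedness. Results below are two-sided unless marked.

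**Inputs for the bias illustration.** From the protocol: 800 enrolled, 1:1, hence 400 per arm; 50% control rate. Assumed, because the protocol does not give them: no true timing effect; share lost before transfer L in each arm; prognosis q of the lost women, meaning the pregnancy rate they would have had.

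**Formula.** Rate among transferred women = (0.5 − L·q)/(1 − L). Rejection is by the pooled two-sided 5% test (equivalent to chi-square) with 400·(1 − L) women per arm.

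Example: L = 0.10 in control, 0.15 in study, q = 0.3 in both. Control: (0.5 − 0.03)/0.90 = 52.22%. Study: (0.5 − 0.045)/0.85 = 53.53%. Difference +1.31 points.

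| Loss, control / study | q, control / study | Rates | Bias (points) | Type I error |
|---|---|---|---|---|
| 10% / 15% | 0.4 / 0.4 | 51.11% / 51.76% | +0.65 | 5.3% |
| 10% / 15% | 0.3 / 0.3 | 52.22% / 53.53% | +1.31 | 6.4% |
| 10% / 20% | 0.4 / 0.4 | 51.11% / 52.50% | +1.39 | 6.5% |
| 10% / 20% | 0.3 / 0.3 | 52.22% / 55.00% | +2.78 | 11.2% |
| 20% / 20% | 0.5 / 0.3 | 50.00% / 55.00% | +5.00 | 24% |
| 10% / 20% | 0.5 / 0.5 | 50.00% / 50.00% | 0 | 5.0% |
| 10% / 20% | 0.7 / 0.7 | 47.78% / 45.00% | −2.78 | 11.2% |

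The fifth row shows that unequal numbers are not needed. The last two show that the bias vanishes when loss is unrelated to prognosis and changes sign when the lost women have the better prognosis.

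**Power, 50% against 60% per transfer, equal non-transfer in both arms.** For all randomised women, each rate is multiplied by (1 − L) and n stays at 400 per arm.

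| Untransferred | Per transfer, n per arm | Power, two-sided | All randomised, rates | Power, two-sided | Power, one-sided |
|---|---|---|---|---|---|
| 10% | 360 | 77% | 45% / 54% | 72% | 82% |
| 20% | 320 | 72% | 40% / 48% | 63% | 74% |

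**The case against.** *Per transfer is the question asked.* Section 2.1 words the objective in terms of transfers timed by the test, and section 7.1 plans on a rate among euploid transfers. This stands as a reason to keep the measure. It does not restore the randomised comparison.

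*Large differential loss is unlikely.* Under section 4.2(c) and (d), every woman has agreed to a mock cycle and a single frozen transfer and has a suitable embryo in hand. This stands in part: it makes large differential loss less likely, but it does not prevent later withdrawal.

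*Analysis populations belong in the SAP.* Many details do, including the handling of unknown outcomes. The denominator does not fall under that heading, since the protocol fixes it in two places.

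Some stronger readings are tempting but unsupported:

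- A reader might infer that the per-transfer rate favours the test. Nothing in the protocol gives the prognosis of the women who leave.
- A reader might take the inadequate-sample rule to remove study women only. Its wording covers any subject, and whether a withdrawn control stays in the denominator is not stated. Nor does the protocol link an inadequate sample to prognosis.
- A reader might take the 10–20% dropout in section 7.1 as a contrast between arms. It is one overall figure and may include loss after transfer.

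**Conclusion.** The point holds, and the protocol should be changed. The stated primary comparison gives up the guarantee that randomisation provides. It does not follow that the result will be biased.

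With no true effect, 50% overall prognosis and 400 per arm, a 5-point difference in loss (10% against 15%) with prognosis of 30–40% among the lost gives 0.7 to 1.3 points and a type I error of 5.3% to 6.4%. At 10% against 20% it is 1.4 to 2.8 points and 6.5% to 11%. Equal 20% loss with prognosis of 50% against 30% gives 5.0 points, half the planned 10-point difference, and about 24%. A reader might take one of these as the worst case; none is an upper limit, because loss by arm and prognosis are assumed throughout. The sign may also be reversed, or the bias zero.

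**What to change.** In section 7.2(a) and the synopsis:

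1. Make the primary comparison all randomised women in the arm assigned.
2. Define the outcome as clinical pregnancy from the first study transfer, within one prespecified window from randomisation that is the same in both arms and long enough for the mock cycle, result, transfer cycle and 6-week scan. The sponsor sets its length. Later transfers do not count. Without this limit, controls, who start a cycle earlier, could have a second transfer inside the window. If, say, 20% of control failures did so with 50% success, the control rate would become 50% + 0.5 × 20% × 50% = 55%, and a null effect would be rejected about 29% of the time.
3. Count women known to have had no study transfer in the window as not having the outcome.
4. Keep women withdrawn under 5.6(c)3) in the analysis, with outcome follow-up where consent allows and no change to clinical management.
5. Do not count unknown outcomes as failures by default. With no true effect and 50% prognosis, 10% against 20% unknown scored as failures would give 45% against 40% and about 30% rejection. The method may be left to the SAP.
6. Keep per transfer as a labelled supportive analysis that matches section 2.1.

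In section 7.1, restate the power within the planned 800 and state the sidedness: with 10–20% untransferred in both arms, about 72–63% two-sided or 82–74% one-sided.

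The cost is protocol wording, outcome retrieval for women without a study transfer, and lower power than per transfer (77–72% two-sided). If more study women truly never reach transfer, for example 15% against 10%, the contrast becomes 0.60 × 0.85 = 51% against 0.50 × 0.90 = 45%, with power of about 40%; that is a real effect of the strategy.

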4.2. Inclusion criteria

- (a) Subjects who have at least one implantation failure with a euploid or low-level mosaic (< 30%) embryo transfer in the past two years.
- (b) Females within 28-45 years old.
- (c) Those who agree to undergo one mock cycle for ora™ test and execute single frozen embryo transfer in the later cycle.
- (d) Those who has at least one remaining euploid or low-level mosaic (< 30%) embryo.

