5.5. Data collection and protection

All data obtained in clinical trials are subject to data protection. The paper informed consent and case report form (CRF) will be stored in a locker on the test facility and/or electronically separately. Investigators/researcher shall not disclose the subject’s name and other identifiable personal data (excluding year of birth/age, weight, height and medical record number (MRN)).

Any documents submitted to Inti Labs do not contain names, but only subject codes. Likewise, data for statistical evaluation can only be accessed under the subject code. Only the researcher can identify the subject's name and other personal information through the code. If the name of a subject needs to be identified for medical reasons during the research, all subjects involved are obliged to keep it confidential.

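### The pregnancy outcomes are compared by a crude chi-square although age and BMI are known before randomisation: a modest, cheaply recovered loss of efficiency, not an error

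*Protocol*

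**What the plan says.** Section 7.2(a) states that clinical pregnancy, live birth and similar outcomes, per transfer, "will be compared between the study and control groups by chi-square analysis". The synopsis covers clinical and ongoing pregnancy in the same sentence, which ends by saying that "live birth rate per transfer will be compared between the study and control groups by chi-square analysis". Neither place names a covariate or a stratified analysis. BMI appears in 7.2(b), but only among quantities to be compared between groups by the Mann-Whitney test.

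The population is broad by design. Section 4.2 admits "Females within 28-45 years old", any number of earlier failed transfers from one upward in the past two years, and women with "at least one remaining euploid or low-level mosaic (< 30%) embryo". Section 4.3 excludes a BMI above 30. Section 5.5 lists the items exempt from its ban on disclosing identifiable data ("excluding year of birth/age, weight, height and medical record number (MRN"), so age, height and weight are clearly held. Section 5.6(a) randomises 1:1 with centre as the only stratification factor. An age category is mentioned there for numbering subjects, not for allocation.

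Section 7.1 calls 325 per group "adequate to detect a 10% difference in clinical pregnancy outcomes between groups". The error rates behind that claim are an alpha of 0.05, with no word on sidedness, and a power of 80%. The control rate is set by "using 50% anticipated LB in the control arm".

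**The concern.** Age and BMI have to be checked before a woman can be randomised, so they exist for everyone at no extra cost. If they predict pregnancy, a comparison that ignores them leaves explainable variation in the standard error. A model with prespecified baseline covariates would remove part of it, including the part due to chance differences in prognosis between the arms.

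The protocol itself names the test, so a plan that used an adjusted model as primary would depart from it. The trial is also unblinded, so covariates chosen after outcomes are known would carry little weight. At stake is some precision in a trial whose two-sided power is already below what section 7.1 states.

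**Working it through.** **Inputs from the protocol (7.1, 5.6):** control rate 50%, difference 10 points, alpha 0.05 with sidedness not stated, power 0.80, 325 per arm, 1:1 allocation.

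**Inputs not in the protocol:** the prognostic strength of any covariate. All R² values below are assumptions.

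**1. The stated sample size.** With pooled variance, n = [z_α√(2×0.55×0.45) + z_β√(0.25+0.24)]²/0.10².
- Two-sided: (1.960×0.7036 + 0.8416×0.7000)²/0.01 gives 388 per arm.
- One-sided: (1.645×0.7036 + 0.8416×0.7000)²/0.01 gives 305 per arm, or 325 with continuity correction.

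The stated 325 is therefore reproduced only as a one-sided 5% test with continuity correction.

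**2. Two-sided power of the crude test at 325 per arm.** The null standard error is √(2×0.55×0.45/325) = 0.0390 and the alternative standard error is √((0.25+0.24)/325) = 0.0388. Power = Φ[(0.10 − 1.96×0.0390)/0.0388] = 72.8%.

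**3. Assumed share of outcome variance explained (outcome variance 0.25).**
- Age, SD 4 years, 1 to 2 points per year: (0.01×4)²/0.25 = 0.006 to (0.02×4)²/0.25 = 0.026.
- Earlier failures, half the women with two or more, 10 to 15 points lower success: 0.25×0.10²/0.25 = 0.010 to 0.25×0.15²/0.25 = 0.023.
- Embryo class, 30% without a euploid embryo, 10 to 20 points lower success: 0.3×0.7×0.10²/0.25 = 0.008 to 0.3×0.7×0.20²/0.25 = 0.034.

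Age and failures together give 0.016 to 0.048. All three give about 0.025 to 0.08. The components are added as if independent; overlap would lower the total. BMI and centre are given no value.

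**4. What adjustment is worth.** Extra women = 650/(1−R²) − 650. Power is that of step 2 with n = 325/(1−R²).

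| Assumed R² | Equivalent extra women | Power |
|---|---|---|
| 0 | 0 | 72.8% |
| 0.016 | 11 | 73.4% |
| 0.025 | 17 | 73.8% |
| 0.048 | 33 | 74.8% |
| 0.08 | 57 | 76.3% |

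Age alone (0.0064 to 0.0256) is worth about 4 to 17 women. Reaching 80% would need R² of about 1 − 325/388 = 0.16.

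**5. Simulation.** There were 325 per arm and 6,000 runs per scenario, comparing the crude test with a logistic Wald test that had one prognostic and three null covariates. Centre was not simulated.

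| R² | Crude power | Adjusted power |
|---|---|---|
| 0 | 73.5% | 72.4% |
| 0.02 | 73.4% | 73.6% |
| 0.06 | 73.7% | 75.0% |
| 0.10 | 74.7% | 77.8% |

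Over all scenarios run, type I error was 5.0-5.8% crude and 4.5-5.4% adjusted.

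**6. Chance imbalance.** Under the step 3 assumptions, imbalance in the three factors moves the crude difference with these SDs, in points:
- Low end: √(0.36² + 0.31² + 0.39²) = 0.62.
- High end: √(0.72² + 0.63² + 0.59²) = 1.12.

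The crude standard error of 3.88 points already contains this. Removing it leaves √(3.88² − 0.62²) = 3.83 to √(3.88² − 1.12²) = 3.72, so intervals become 1% to 4% narrower. This is the gain of step 4 seen from another side, not a second gain.

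**The case against.** The strongest reply is that nothing in 7.2 is wrong. A crude chi-square is a valid test in a 1:1 randomised trial, and the simulated type I error bears that out. Covariate lists, effect measures and supporting models also commonly sit in an analysis plan, which is not shown here. Both points stand, and they limit this to an efficiency point. They do not remove it, because the protocol fixes the unadjusted test in two places.

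Several stronger readings are tempting, and the protocol does not support them:

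- **That every useful covariate is known for each woman before randomisation.** This is shown for age and BMI. For earlier failures, eligibility requires only one or more, and no section says that the count is recorded. For embryo class, section 4.2(d) and part of 5.1 admit women whose remaining embryo is low-level mosaic. The synopsis design text, the arm descriptions in 5.1 and the transfer step in 5.6(d) speak of euploid embryos. These passages must be reconciled before the class has a clear meaning as a covariate. A woman may also hold both kinds, so the class transferred can be settled after randomisation.
- **That chance imbalance of up to 1.2 to 2.2 points (about two SDs from step 6) is bias on top of the power loss.** It is already inside the crude standard error.
- **That the plan will give only a p-value.** Section 7.2 names a test and does not rule out an estimate with an interval; that inference rests on silence.

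The reply is also right that a model with prognostic covariates but without centre would still ignore the only stratification factor.

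**Conclusion.** The point holds as a modest loss of efficiency. The protocol fixes an unadjusted comparison of the pregnancy outcomes while holding at least two baseline covariates that could be used without new data. The gain is 0.7 to 2.1 power points if age and failure count carry the assumed strengths, and at most about 3.5 points if embryo class is added. It is less if age alone is prognostic, and zero or slightly negative if nothing is. The range rests wholly on assumed prognostic strengths, additive components and a two-sided 5% test of 50% against 60% with 325 evaluable women per arm.

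A reader might infer that adjustment repairs the sample size. It does not: an R² of about 0.16 would be needed, twice the top of the assumed range. The gap between 72.8% and 80% is a separate matter of the sidedness and sample size in 7.1.

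**What to change.** Before any outcomes are seen, amend 7.2 and the synopsis, and carry the change into the analysis plan:

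- Make the primary analysis a logistic model of clinical pregnancy on arm, age (continuous), BMI and centre, with small centres pooled by a prespecified rule.
- Report the standardised (marginal) risk difference with its 95% confidence interval and test.
- Add the number of earlier failed transfers, and the embryo class available at eligibility, only if each is recorded on the CRF before randomisation. Use the class available at eligibility, not the class later transferred. Add embryo class only once the synopsis, 4.2, 5.1 and 5.6(d) agree on whether low-level mosaic embryos are transferred.
- Analyse ongoing pregnancy and live birth in the same way, and keep the chi-square as a sensitivity analysis.

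The cost is a paragraph of text, covariates named in advance, possibly one extra CRF field, and up to about one point of power if the covariates turn out not to be prognostic. No extra visits or women are needed.
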